#### **4.3. Post-Operative Inclusion Criteria**

1. Subjects must report “moderate” to “severe” baseline pain within 6 hours post-surgery, as characterized on a 4-point categorical pain intensity scale (0= none, 1= mild, 2= moderate, 3= severe)
2. Subjects must report a score on the 11-point Numerical Pain Rating Scale (NPRS) of  $\geq 5$  within 6 h post-surgery, where 0 represents ‘No pain’ and 10 represents ‘worst pain imaginable’ at study baseline.
3. Subject has had no evidence of any clinically significant abnormality during or following surgery that, in the judgment of the investigator, significantly increases the risks due to study participation.
4. In the judgment of the investigator, study participation would not put the subject at risk from the specified surgical procedure, anesthetic protocol, or specified analgesic regimen.

#### **4.4. Discontinuation of Subjects**

##### **4.4.1. Procedures for Withdrawal**

A subject may request to be withdrawn from study participation at any time, without disclosing the reason if chosen not to. Subject may be discontinued from the study by the Investigator or the Sponsor at any time if either determines that it is not in the Subject’s best interest to continue participation or due to non-compliance with the protocol. Investigator is encouraged to contact the study Medical Monitor to discuss details surrounding non-compliance. Subjects who withdraw consent to continue treatment or who are discontinued from the study before completing the protocol-specified duration of treatment should be encouraged to complete the early termination assessments and procedures outlined for 8 hours after treatment initiation. Subjects will be encouraged to agree to return to the study site 7 days ( $\pm 3$  days) post-surgery for evaluation of their safety and well-being. The date the subject is withdrawn and the primary reason for discontinuation will be recorded in the subject’s case report form (CRF).

##### **4.4.2. Replacement of Subjects**

Subjects who discontinue after randomization will not be replaced in this study.

**4.5. Lifestyle Guidelines**

**4.5.1. Confinement**

Prior to the surgical procedure (Day 1), subjects will arrive at the study clinic to prepare for the procedure and confirm eligibility to participate in the study. Following the third molar extraction procedure, subjects who achieve adequate pain intensity will be randomized and initiate dosing with study drug. Subjects may be discharged from the study clinic about 8 hours after receiving the study drug treatment. For safety and welfare of the subject, the site may choose to have subjects stay overnight. Subjects will be allowed to ambulate normally as per standard of care instructions after surgery.

**4.5.2. Diet**

Subjects will remain NPO (nothing by mouth), including water, from check-in (i.e., at least 2 hours before the administration of the dose of study medication to randomized subjects) until 2 hours post-dose, on Day 1 (study day). After 2 hours post-dose, subjects will be permitted to consume water, or gelatin snacks. Subjects are prohibited from ingesting solid foods or carbonated beverages for at least 6 hours post-dose.

## **5. TREATMENTS**

### **5.1. Surgical Procedure**

Study staff will verify admission and surgery schedule the day of the scheduled procedure. Subjects who continue to meet all eligibility requirements for study enrollment are eligible to receive study drug as long as the Post-Operative Inclusion Criteria are met.

#### **5.1.1. Anesthetic Care**

The subject may be administered local anesthesia with Lidocaine 2% with epinephrine with (maximum volume of 20 mL). Nitrous oxide and benzocaine gel are allowed. Sedation will not be allowed. Long acting local anesthetics (e.g. bupivacaine and ropivacaine) and steroids are also prohibited.

#### **5.1.2. Surgery**

Surgical removal of the impacted third molars will be carried out per the surgeon's standard of care practice. Two (2) mandibular third molar teeth will be extracted. The mandibular third molars must involve a full or partial bony impaction confirmed by radiographic evidence. Extraction of 1 or 2 impacted or non-impacted maxillary third molars as part of the surgical procedure is permitted but not required.

#### **5.1.3. Post-operative Care**

It is anticipated that subjects will receive study medication once subject meets the post-operative inclusion criteria. Post-surgical follow-ups will be scheduled 7 days ( $\pm 3$  days) post-surgery for evaluation of their safety and well-being.

## **5.2. Disallowed medications**

- Except as indicated in the rescue analgesic regimen, any additional analgesic (morphine, ketorolac, ibuprofen, acetaminophen etc.).
- General anesthesia, long acting local anesthetics (e.g. bupivacaine, ropivacaine) or other sedative medications.

## **5.3. Administration of Study Medication**

Study drug will be administered as follows:

1. Subject must be in an upright position before administering study drug.
2. Study drug will be administered to the subject by qualified medical staff.
3. Subjects will receive a single dose of the assigned study treatment (DFN-15 [62.5 mg, 125 mg, or 250 mg] or placebo) administered, as a total volume of 10 mL, according to the randomization number.

## **5.4. Identity of Study Medication**

DFN-15 is an oral solution containing 25 mg/mL of celecoxib. Each mL of DFN-15 will contain 25 mg celecoxib. DFN-15 will also contain the inactive ingredients, lauroyl polyoxylglycerides, glyceryl caprylate, caprylic/capric triglyceride, polyoxyl 35 castor oil, polyoxyl 40 hydrogenated castor oil, propyl gallate, menthol, magnasweet, sucralose,

## PROTOCOL DFN-15-CD-010

acesulfame potassium, peppermint flavor, banana flavor, bubble gum flavor, glycerol, ethanol, and water.

DFN-15 and matching placebo are packaged in amber-colored glass bottles containing 4.8 mL solution per bottle (120 mg) and equipped with child-resistant and tamper-evident caps.

A 6-month accelerated and 12-month real time stability data from the clinical batch meets stability specifications. The drug product for the clinical study will be continued to be supported with appropriate stability testing for the duration of any clinical study.

The DFN-15 formulation and the matching placebo are manufactured for the Reddy's Laboratories Limited by: Contract Pharmaceuticals Limited Canada, [name]

The active pharmaceutical ingredient for DFN-15 is manufactured for [name] by: Hetero Drugs, Ltd., [name]. Manufacturing of the study drug was performed according to Good Manufacturing Practice for Medicinal Products and all relevant regulatory requirements.

### **5.5. Method of Assigning Subjects to Treatment Groups**

A computer-generated randomization scheme will be prepared prior to study initiation. Subjects will be randomly assigned to treatment with DFN-15 62.5 mg, DFN-15 125 mg, DFN-15 250 mg, or placebo in a 1:1:1:1 assignment ratio according to the randomization scheme. All study doses administered will be according to the treatment assignment. Male and female subjects (approximate ratio of 1:1) who meet all of the inclusion criteria (including postoperative inclusion criteria) and none of the exclusion criteria will be stratified.

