Study Visits:	
Total number of visits to the clinical facility: 3
 
Visit no. 1 (Day -28 to Day -1): Screening
 
Visit no. 2 (Day 1): Bilateral mandibular third molar extraction surgery, followed by randomization, administration of study treatment and observation in the clinical facility for 8 hours post dose. Subjects will be confined within the clinical study facility for at least 8 hours post-dose.

	
No overnight stay at the research facility will be required, however if it is clinically appropriate to do so, subjects should remain at the research center until they are safe to leave.
 
Visit no. 3 (Day 4 to Day 10): Follow-Up visit

Study Population:	Male and female subjects (approximate ratio of 1:1) who meet all of the inclusion criteria (including postoperative inclusion criteria) and none of the exclusion criteria below.

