### **8.3. General Considerations for Statistical Analysis**

#### **8.3.1. Analysis Datasets**

Modified Intent-to-Treat (mITT) Analysis Set: The mITT set will include all subjects who receive study drug, and have recorded at least one post dosing efficacy score.

Safety Set: The safety set will include all treated subjects and will be used for safety and tolerability assessments.

Pharmacokinetic Set: The pharmacokinetic set will include all subjects who have received a dose of DFN-15 and have at least one quantifiable concentration of celecoxib in plasma.

Non-compartmental analysis as specified in a PK Analysis Plan will be used to estimate pharmacokinetic parameters and to present descriptive statistics using the Pharmacokinetic Set. Additional exposure-response analysis may be built in the full statistical analysis plan (SAP). Comparisons will be performed at the 0.05 two-sided significance level unless otherwise specified. No adjustments for multiplicity will be performed. Additional details of the analysis will be provided in the SAP and/or the clinical study report. The SAP will supersede the protocol in case of a discrepancy.

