#### **8.5. Efficacy Analysis**

##### **8.5.1. SPID and PID Analyses**

Time weighted SPID6 is the primary efficacy endpoint. The difference among the treatment groups for the primary endpoint, as well as the secondary endpoints of SPID2, SPID4 and SPID8 will be evaluated using analysis of variance. Model will be an ANCOVA with treatment as main effect, and baseline PI as a covariate. If multiple centers are enrolled, then center may be added as an exploratory factor and the interaction with treatment will be explored.

A sensitivity analysis will be performed to examine the interaction between the treatment and analysis center. If the interaction is considered significant at 0.10 significant level a subgroup analysis by analysis center will be performed to examine the treatment effect at each site in order to understand the nature of the interaction between the treatment and analysis center.

Analgesic effect of DFN-15 at each dose level compared to placebo will be evaluated using Dunnett's test.

PID at each time point will be summarized with descriptive statistics (sample size, mean, standard deviation, median, minimum, and maximum) for each treatment group; change from baseline within a group will be tested with 1-sample *t*-test. Group mean by time profile will be graphically presented for pain intensity measurements.

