2.5 Randomization

A computer-generated randomization scheme will be prepared prior to study initiation.

Subjects will be randomly assigned to treatment with DFN-15 62.5 mg, DFN-15 125 mg, DFN-15 250 mg, or placebo in a 1:1:1:1 assignment ratio according to the randomization scheme. Randomization will occur after the subject has qualifying baseline pain, other post-operative inclusion criteria are met, and all Pre-Dose Baseline assessments have been performed on Day 1. All study doses administered will be according to the treatment assignment. No stratification will be performed as part of the randomization; however, male and female subjects will be enrolled in an approximate ratio of 1:1. Subjects who discontinue after randomization will not be replaced in this study.

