8.2.2 Summed Pain Intensity Difference

The primary efficacy endpoint is the summed pain intensity difference over the first 6 hours (SPID₆) between each of the DFN-15 dose levels and placebo. SPID₆ is created by summing the time weighted pain intensity differences (PID) scores using the area under the PID curve methodology.

All SPID calculations will be done using the standard trapezoidal rule:

SPIDx =

$$\sum_{i=0}^{x} \left(\frac{PID_i + PID_{i+1}}{2} \right) * (T_{i+1} - T_i)$$

Where: $PID_i = P_i - PIBL$ (Pain Intensity score at time i and Pain Intensity score at Baseline), $(T_{i+1} - T_i)$ is the Time difference in minutes between time i and time i+1, and $(T_{i+1} - T_i)$ is the Time difference in minutes between time i and time i+1.

Baseline PI will be defined as the last PI recorded prior to first dose. Time points will be selected for inclusion into specific SPID periods based on nominal time points (e.g., all scheduled assessments from Baseline to the Hour 6 assessment will be included in SPID₆).

Except for baseline, the actual date/times of assessments will be used in the SPID calculation whenever collected. For baseline, rather than the actual time recorded, baseline pain will be considered to be recorded at time 0(i.e., time of first dose).

All imputation, as described in Section 8.1.1, will be performed prior to the SPID calculations.

The individual SPID variables will also be presented in subject listings.

The secondary efficacy SPID outcomes (SPID₂, SPID₄, and SPID₈) are calculated similarly to SPID6 adjusting for the respective time periods.

All SPID endpoints will be analyzed using an ANCOVA with treatment as the main effect and both baseline pain intensity and BMI as covariates. Mean SPID values over time will be displayed graphically.

The results of the ANCOVA will be presented in summary tables with standard summary statistics as well as least square (LS) means, active dose level vs. placebo LS mean differences

(treated group – placebo), standard errors, confidence intervals (CI) and paired-comparison p-values with Dunnett's test.

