8.2.5 Total Pain Relief (TOTPAR)

Total Pain Relief (TOTPAR) over 2, 4, 6, and 8 hours. Total pain relief is calculated similarly to SPID replacing the PID values with the pain relief (PR) scores on the 5-point scale where 0= no pain relief, 1= little pain relief, 2= some pain relief, 3= a lot of pain relief, and 4= complete pain relief. All imputation, as described in Section 8.1.1, will be performed prior to the TOTPAR calculations.

All TOTPAR endpoints will be analyzed using an ANCOVA with treatment as the main effect and baseline pain intensity and BMI as covariates. The results of the ANCOVA will be presented in summary tables with standard summary statistics as well as least square (LS) means, active dose level vs. placebo LS mean differences (treated group – placebo), standard errors, confidence intervals and paired-comparison *p*-values with Dunnett's test. Mean TOTPAR values over time will also be displayed graphically.

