15.0 Appendices

15.1 Tables for Final Study Report

Number	Title	Analysis Population
Study Population		
14.1.1	Summary of Subject Disposition	All Subjects
14.1.2.1	Summary of Demographic and Baseline Characteristics	mITT Population
14.1.2.2	Summary of Demographic and Baseline Characteristics (if applicable)	Safety Population
14.1.3	Summary of Medical History	Safety Population
14.1.4	Summary of Concomitant Medications by Drug Class and Medication	Safety Population
14.1.5	Summary of Concomitant Medications by Drug Class and Medication after Discharge	Safety Population
Efficacy	•	·
14.2.1.1	Primary Endpoint: Analysis of Summed Pain Intensity Difference from T0 to T6 (SPID6)	mITT Population
14.2.1.2	Analysis of Summed Pain Intensity Difference from T0 to T6 (SPID6)	PP ['] Population
14.2.1.3	Analysis of Summed Pain Intensity Difference from T0 to T6 (SPID6) by Gender	mITT Population
14.2.1.4	Analysis of Summed Pain Intensity Difference from T0 to T6 (SPID6) by Qualifying Pain Intensity	mITT Population
14.2.1.5	Analysis of Summed Pain Intensity Difference from T0 to T6 (SPID6) by BMI Category	mITT Population
14.2.1.6	Analysis of Summed Pain Intensity Difference from T0 to Other Timepoints (SPID2, SPID4, SPID8)	mITT Population
14.2.1.7	Analysis of Summed Pain Intensity Difference from T0 to Other Timepoints (SPID2, SPID4, SPID8)	PP Population
14.2.2	Summary of Pain Intensity and Pain Intensity Difference by Timepoint	mITT Population
14.2.3	Summary of Pain Intensity and Pain Intensity Difference by Timepoint	PP Population
14.2.4	Analysis of Proportion of 30% and 50% Responders (NPRS)	mITT Population

Number	Title	Analysis
14.2.5.1	Summary of Pain Relief by Timepoint	Population mITT
14.2.5.2	Summary of Pain Relief by Timepoint	Population PP
14.2.5.3	Analysis of Total Pain Relief (TOTPARx)	Population mITT
14.2.5.4	Analysis of Total Pain Relief (TOTPARx)	Population PP
14.2.6.1	Summary of Peak Pain Relief	Population mITT
14.2.6.2	Summary of Peak Pain Relief	Population PP
14.2.7.1	Analysis of Time to Peak Pain Relief	Population mITT
14.2.7.2	Analysis of Time to Peak Pain Relief	Population PP
14.2.8.1	Proportion of Subjects Satisfied with Treatment	Population mITT
14.2.8.2	Analysis of Subject Treatment Satisfaction	Population mITT
14.2.9	Analysis of Time to Perceptible Pain Relief	Population mITT
14.2.10	Analysis of Time to Meaningful Pain Relief	Population mITT
14.2.11	Analysis of Time to First Use of Rescue Medication	Population mITT

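### Protocol 5.5 and SAP 2.5 give opposite accounts of stratification by sex; the randomization specification must settle it, and the effect on the analysis is minor

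*Protocol*

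**What the plan says.** Protocol 5.5, on assigning subjects to treatment, provides for a computer-generated 1:1:1:1 scheme made before the study starts. It ends by saying that male and female subjects, in an approximate 1:1 ratio, "who meet all of the inclusion criteria (including postoperative inclusion criteria) and none of the exclusion criteria will be stratified". The section gives no strata and no block sizes.

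SAP 2.5 describes the same scheme and says: "No stratification will be performed as part of the randomization; however, male and female subjects will be enrolled in an approximate ratio of 1:1".

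The analysis models contain no sex term. SAP 8.2.2: "All SPID endpoints will be analyzed using an ANCOVA with treatment as the main effect and both baseline pain intensity and BMI as covariates". SAP 8.2.5: "All TOTPAR endpoints will be analyzed using an ANCOVA with treatment as the main effect and baseline pain intensity and BMI as covariates". The ANCOVAs for PID by timepoint (SAP 8.2.1) and for the satisfaction score (SAP 8.2.8) use the same two covariates. In the efficacy analysis sex appears only as a SPID6 subgroup, in the table titled "Analysis of Summed Pain Intensity Difference from T0 to T6 (SPID6) by Gender".

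On precedence, Protocol 8.3.1 says: "The SAP will supersede the protocol in case of a discrepancy". The synopsis says the same. SAP 13.0, on changes from the protocol, does not mention stratification, and neither does the SAP document history.

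**The concern.** Both sentences are current text, and they cannot both describe one list. The precedence clause decides which document governs the analysis. It cannot decide how a list made before the study started was generated.

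The answer bears on the standard error. Stratifying by sex removes between-sex variation from the treatment contrasts. If sex predicts pain and is left out of the model, that variation stays in the residual, so the reported standard error exceeds the true one and the test runs below its nominal level. The study report must also state one randomization method.

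**Working it through.** **1. The texts side by side.** The last sentence of Protocol 5.5 repeats the Study Population entry of the synopsis, "Male and female subjects (approximate ratio of 1:1) who meet all of the inclusion criteria", and adds the stratification verb. Other parts of the protocol that would reflect a sex stratum do not:
- The synopsis (Trial Design) and Section 3.1 describe 1:1:1:1 randomization without strata.
- The primary model in the synopsis omits sex, as does Section 8.5.1: "Model will be an ANCOVA with treatment as main effect, and baseline PI as a covariate". The only further factor that 8.5.1 allows for is center.
- Section 8.5.3 would stratify the log-rank test by center only.

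These favour a misworded enrolment target, but they are indirect.

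**2. Inputs for the size of the effect.** The sample size has no formal calculation, so there is no figure of the plan's to reproduce.
- 120 subjects at 1:1:1:1 (Protocol synopsis): 120/4 = 30 per arm.
- Two-sided 0.05 (SAP 3.0); Dunnett's test for three doses against placebo (SAP 8.3).
- Residual df: 120 − 4 − 2 = 114, or 113 with sex. Dunnett critical values: 2.3807 and 2.3810.
- The effect of sex on SPID6 is **not in the documents**. Assumed share of residual variance explained: R² = 0, 1, 2, 5, 10%. At a 1:1 split the male-female difference is 2√R² residual SDs.

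**3. Mechanism.** Set the residual variance after baseline pain and BMI to 1. With 15 men and 15 women in each arm, the true variance of a dose-placebo difference is about (1 − R²) × 2/30. The model without sex estimates about 1 × 2/30. The test therefore behaves as if its critical value were 2.3807/√(1 − R²):
- R² = 2%: 2.3807/√0.98 = 2.405, familywise error about 0.047
- R² = 5%: 2.3807/√0.95 = 2.443, about 0.043
- R² = 10%: 2.3807/√0.90 = 2.510, about 0.036

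With an unstratified list, chance imbalance in sex adds to the true variance as well, so the model's standard error is right on average.

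**4. Simulation.** 100,000 runs per cell, Monte Carlo SE 0.0007. Stratified means 15/15 per arm; unstratified means 60/60 overall, allocated at random. The middle three columns are familywise error. The last is interval width without sex divided by width with sex, for a stratified list.

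| R² | Sex difference (SD) | Stratified, sex omitted | Stratified, sex included | Unstratified, sex omitted | Width ratio |
|---|---|---|---|---|---|
| 0 | 0 | 0.0499 | 0.0499 | 0.0504 | 0.9998 |
| 1% | 0.200 | 0.0471 | 0.0485 | 0.0496 | 1.0050 |
| 2% | 0.283 | 0.0473 | 0.0501 | 0.0501 | 1.0103 |
| 5% | 0.447 | 0.0432 | 0.0506 | 0.0505 | 1.0267 |
| 10% | 0.632 | 0.0364 | 0.0504 | 0.0501 | 1.0558 |

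At R² = 10%, stratified with sex omitted, the mean model SE is 0.2603 and the actual SD of the estimate is 0.2466, a ratio of 1.056. Step 3 predicts 1/√0.90 = 1.054. For an unstratified list the two are 0.2599 and 0.2608.

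**5. Power.** Assume a 0.75 SD effect of one dose (50,000 runs). Adding sex changes power as follows:
- R² = 5%: 0.695 to 0.717 if stratified, 0.690 to 0.712 if unstratified.
- R² = 10%: 0.698 to 0.742 if stratified, 0.692 to 0.739 if unstratified.

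The gain is about the same with either list.

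**The case against.** The strongest reply is that the documents largely settle this themselves. The SAP was written after review of Protocol Version 2.0. Its section 2.5 takes up the same two subjects as Protocol 5.5, stratification and the sex ratio, and reads as a clarification. The SAP takes precedence, and its models fit an unstratified design. One verb in one protocol sentence is the only support for a sex-stratified list. The study is described as exploratory (Protocol 5.6) and its sample size is empirical.

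Most of this stands, and it makes the unstratified reading the likelier one. It does not remove the need to look at the specification, because neither document is the list. If the SAP is right, Protocol 5.5 is still wrong as written.

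The size in the working is also close to an upper case for each assumed R². It takes exact sex balance in every arm, whereas the plan promises an approximate ratio, possibly over one to three centers, and analyses the mITT set. Less exact balance shrinks the conservatism.

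A reader might infer three stronger points that the documents do not support:
- **That the list was stratified and the SAP ignores it.** Nothing beyond that one sentence says so.
- **That the planned SPID6 test is biased or exceeds 0.05.** It does neither under either reading.
- **That the contradiction costs power which a sex term would recover.** The gain is the ordinary gain from a prognostic covariate and does not depend on stratification.

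**Conclusion.** The contradiction is real and unrecorded, and its consequence is minor. If the list was unstratified, which is the likelier reading, the planned models hold their level and only Protocol 5.5 needs correcting. If it was stratified and sex is prognostic, the SPID and TOTPAR tests are mildly conservative: familywise error about 0.047, 0.043 and 0.036 at an assumed 2, 5 and 10% of residual variance, with intervals about 1.0, 2.7 and 5.6% wider than with sex in the model. The effect is negligible up to 2%. The 10% case needs a male-female difference of 0.632 SD, which is 0.632/0.75 = 84% of the drug effect assumed in the power runs. These figures rest on assumed sex effects and near-exact balance per arm. Confidence is high for the conflict between the texts and low that any result would change.

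**What to change.** Before unblinding:
1. Check the specification from which the randomization list was generated.
2. Correct whichever of Protocol 5.5 or SAP 2.5 is wrong, and record the resolution in SAP 13.0.
3. If the list was stratified by sex, add sex as a fixed factor to all ANCOVAs that share the covariate set: SPID (8.2.2), TOTPAR (8.2.5), PID by timepoint (8.2.1) and the satisfaction score (8.2.8). Changing only the first two would leave the models inconsistent.
4. If it was not stratified, keep the planned models. Adding sex would still be valid, but it would be an optional efficiency choice that nothing in the documents calls for.

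The cost is one corrected sentence and one entry in SAP 13.0. If the list was stratified, there is also one model factor, using 1 of 114 residual df. Sex is already collected and already used for the SPID6 subgroup table. Settling this before unblinding keeps the choice of model prespecified.
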